## 13.1.3 Planned number of subjects in each site

It is planned to enroll approximately 7 to 12 patients at each study site.

## 13.1.4 Applicable level of significance

The observed differences will be considered statistically significant at the two-tailed 5% significance level. In view of the exploratory nature of the study, no corrections for multiple comparisons are planned.

### 13.1.5 Study termination criteria

Statistical criteria for early termination of the study are not provided for in the present study.

#### 13.1.6 Missing data

Efficacy data

All efficacy data recorded for a patient after the use of the rescue medication or a prohibited drug with an analgesic effect by the patient will be considered missing.

The baseline observation carried forward method (BOCF) will be used to impute missing data for the main efficacy analysis. This method assumes that missing patient data will be replaced with a baseline value from the time patients withdraws from the study or the rescue medication use is started.

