- Patient assessment using the TB risk assessment questionnaire;
- Measurement of height and weighing, calculation of body mass index (body mass index must be assessed before randomization);

CONFIDENTIAL P. 49 of 84

- Dispensing questionnaires to the patient to record the following:
  - o Pain intensity in the assessed joint according to VAS (screening score);
  - Health assessment questionnaire score (baseline value);
- Physician assessment of the degree of swelling, tenderness, erythema and movement restriction in the assessed joint (baseline value);
- Blood sampling for the following analyses:
  - O Diagnosis of infections: HIV, HBsAg and HCV Ab (rapid tests, the results must be evaluated before randomization);
  - o Diagnosis of infections: HIV, HBsAg, HCV Ab (central laboratory);
  - o Complete blood count with WBC differential (absolute neutrophil count, leukocyte and platelet counts must be assessed prior to patient randomization);
  - O Blood creatinine level (local laboratory, creatinine levels must be assessed prior to patient randomization);
  - O Diagnosis of tuberculosis: T-SPOT.TB test performed at screening or during the hospital stay (central laboratory);
  - Calculation of creatinine clearance (automatically in CRF using the Cockcroft-Gault formula);
  - o Blood chemistry with blood lipids (central laboratory);
  - Blood clotting tests (central laboratory);
  - Baseline sample for hs-CRP (central laboratory);
  - Baseline sample for serum amyloid protein A (central laboratory);
  - Baseline sample for cytokines (central laboratory);
  - O Serum pregnancy test for women of childbearing potential (the results must be assessed prior to patient randomization);
- Urinalysis;
- Physical examination (the results must be assessed prior to patient randomization);
- Vital signs (the results must be assessed prior to patient randomization);
- 12-lead ECG (the results must be assessed prior to patient randomization);
- Chest X-ray in 2 views (the results must be assessed prior to patient randomization);
- Serious adverse event recording;
- Eligibility assessment.

For patients meeting the eligibility criteria, the following procedures are performed immediately prior to randomization:

• Handing over to the patient a questionnaire for recording pain intensity in the assessed joint according to the VAS (baseline value recorded immediately (within 1 hour) before randomization).

CONFIDENTIAL P. 50 of 84

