# 10.4 Assessment of efficacy parameters before using the rescue medication

In this study, patients with unbearable pain are allowed to use the rescue medication no earlier than 2 hours after administration of the investigational drug. For such patients, it is necessary to carry out the following procedures:

- Before using the rescue medication, dispensing questionnaires to the patient to record the following:
  - o Pain intensity in the assessed joint according to VAS;
  - o Patient global assessment of the efficacy using a categorical scale;
- Registering the time of use of the rescue medication and enter the results in the source documentation and CRF.

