## 11.4.2 Patient global assessment of efficacy

All randomized patients evaluate the efficacy of their prescribed therapy. The patients perform global assessment of efficacy at 15, 30, 45 minutes, 1, 1.5, 2, 4, 8, 24, 48, 72 hours, 5, 6, 10, 15, 18, 22, 29 and 45 days after the start of the investigational product use. In case of the use of the rescue medication, global assessment of efficacy must be carried out before its administration.

For global assessment of efficacy, patients use a categorical scale with 5 response options. For each assessment of response to therapy, the patient records the result of the assessment in the patient questionnaire.

Completed questionnaires should be dated with indication of time and signed by the patient.

CONFIDENTIAL P. 62 of 84

When handing over the questionnaires to patients outside the study site, the investigator will instruct them on proper completion.

Patient questionnaires and instructions for completion are provided in a separate document.

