# Secondary efficacy endpoints

- Change in pain intensity in the assessed joint at 15, 30, 45 minutes, 1, 1.5, 2, 4, 8, 24, 48, 72 hours, on days 5, 6, 10, 15, 18, 22, 29 and 45 after start of the investigational product therapy compared to baseline (as measured on VAS).
- Proportion of patients who rated the response to the investigational product therapy as "Excellent" or "Good" at 15, 30, 45 minutes, 1, 1.5 hours, 2, 4, 8, 24, 48, 72 hours, on days 5, 6, 10 15, 18, 22, 29, and 45 after initiation of the investigational product therapy;
- Change in the degree of swelling, tenderness, erythema in the assessed joint at 24, 48, 72 hours, on days 5, 6, 10, 15, 18, 22, 29 and 45 after start of the investigational product therapy compared to baseline;

CONFIDENTIAL P. 74 of 84

- Change in movement restriction in the assessed joint at 24, 48, 72 hours, on days 5, 6, 10, 15, 18, 22, 29 and 45 after start of the investigational product therapy compared to baseline:
- Time to 50% reduction in pain intensity in the assessed joint relative to the baseline level according to the VAS;
- Time to use of the rescue medication
- The proportion of patients who received the rescue medication within 72 hours of starting the investigational product therapy and over the entire treatment period;
- Changes in the health assessment questionnaire scores 2, 4, and 6 weeks after start of the investigational product therapy compared to baseline.

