# 13.5.3 Analysis of other efficacy endpoints

All results of patient assessment of pain intensity in the assessed joint on VAS will be presented by measurement points and treatment groups using descriptive statistics.

For all patient assessments of pain intensity in the assessed joint on VAS, pain intensity versus time by the treatment groups will be plotted.

Model means of changes from baseline in pain intensity in the assessed joint on VAS and confidence intervals for pairwise differences between each RPH-104 treatment group and the Voltaren® (diclofenac) group will be presented for each measurement point using repeated measures ANOVA. A model for assessing differences between groups will be selected after assessment of the primary endpoint.

The patient's response to therapy will be presented as frequency tables by assessment point and therapy group.

The results of assessing the degree of swelling, tenderness, erythema and movement restriction in the assessed joint will be presented as frequency tables by points of assessment and treatment groups.

Changes in the degree of swelling, tenderness, erythema and movement restriction in the assessed joint from baseline will also be presented as continuous variables using descriptive statistics by measurement points and treatment groups.

Graphs of changes in the parameters versus time by the treatment groups will be plotted for changes in the degree of swelling, tenderness, erythema and movement restriction in the assessed joint from baseline.

The analysis of time to 50% reduction in pain intensity in the assessed joint will be carried out using the Kaplan-Meier method. Comparison between groups will be carried out using a log-rank test.

CONFIDENTIAL P. 75 of 84

More details on the efficacy endpoint analysis methods will be described in the statistical analysis plan, which will be developed and approved prior to the data lock point for interim analysis.

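### Section 13.1.6 voids patient global ratings after rescue or a prohibited analgesic, but no denominator is fixed for the Excellent/Good proportion, so treatment failures can drop out of it

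*Combined protocol and SAP*

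**What the plan says.** Section 13.1.6 handles efficacy data in three sentences.

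- The first makes missing "All efficacy data recorded for a patient after the use of the rescue medication or a prohibited drug with an analgesic effect".
- The second names BOCF, which "will be used to impute missing data for the main efficacy analysis". It does not say which analysis that is.
- The third explains that values are "replaced with a baseline value from the time patients withdraws from the study or the rescue medication use is started". A prohibited analgesic is not listed there.

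For the patient global assessment, section 11.4.2 says: "The patients perform global assessment of efficacy at 15, 30, 45 minutes", and continues to Day 45. The screening-day list in section 10.2 hands out only the pain VAS and the HAQ. The time-0 cell for the global assessment in Table 3.1 points to footnote 8, which schedules the ratings from 15 minutes to 1.5 hours after dosing. No pre-dose rating is planned.

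Under section 10.4, patients with unbearable pain are "allowed to use the rescue medication no earlier than 2 hours after administration of the investigational drug".

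The secondary endpoint in section 13.5.1 is the "Proportion of patients who rated the response to the investigational product therapy as" Excellent or Good at each time point. Section 13.5.3 says only that the patient's "response to therapy will be presented as frequency tables by assessment point and therapy group". Neither section states a denominator. Section 13.1.1 defines the efficacy population as randomized, dosed patients with at least one VAS pain score after the start of therapy.

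**The concern.** A patient who needs rescue is, for the global assessment, a treatment failure. Section 13.1.6 removes that patient's later ratings and provides nothing usable in their place. If the frequency tables are then built on the ratings that remain, the patients who did worst leave the table, and the proportion responding rises with the amount of rescue.

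The 72-hour pain endpoint would treat the same patient in the opposite way, because BOCF scores the change as zero. Time to rescue and the proportion rescued are separate endpoints. They would show that rescue differed between arms, but they do not correct the responder table.

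Unequal rescue is plausible on the protocol's own reasoning. Section 4.6 expects the target concentration about 2 hours after 4 mg but in under 30 minutes at 20 mg and above. This gives a reason to expect a difference, not evidence of one.

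Timing adds some weight: section 4 says that the interim report on 47 patients may become final.

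**Working it through.** **How much of the schedule is exposed.** The ratings are at 15, 30 and 45 minutes and 1, 1.5, 2, 4, 8, 24, 48 and 72 hours (11), then Days 5, 6, 10, 15, 18, 22, 29 and 45 (8), which makes 19. Rescue from 2 hours can void every rating from 4 hours on: 5 on the hourly schedule plus 8 by day, so 13 of 19.

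**Size in one arm.** The plan gives no figure to reproduce here. Let *n* = 14 (section 13.1.2), *k* patients be voided, and *p* be the proportion Excellent/Good among the rest. Both *k* and *p* are assumptions.

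- Observed cases: *p*
- All patients, voided counted as non-response: *p*(14 − *k*)/14
- Gap: *p* × *k*/14

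| Voided of 14 | All-patient figure at *p* = 70% | Gap for *p* = 50% to 80% |
|---|---|---|
| 2 | 60% | 7.1 to 11.4 points |
| 4 | 50% | 14.3 to 22.9 points |
| 6 | 40% | 21.4 to 34.3 points |

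In whole patients: with 4 voided and 7 responders among the other 10, the table shows 70% on observed cases and 7/14 = 50% over everyone.

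**Size between arms.** Take *k* = 1 in one arm and *k* = 5 in the other, with the same *p* in both.

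- *p* = 70%: 0.70 × 13/14 = 65.0% against 0.70 × 9/14 = 45.0%, a difference of 20.0 points
- *p* = 50%: 46.4% against 32.1%, 14.3 points
- *p* = 80%: 74.3% against 51.4%, 22.9 points

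The observed-case difference is 0 each time. That follows from assuming equal *p*; the example shows what such a table can hide, not what it will hide.

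**At the interim.** If Period 1 filled its 22 places, 47 − 22 = 25 patients were split 2:2:2:2:1, or 25 × 2/9 = 5.6 per higher-dose arm. This is an inference, not a documented count. With 6 per arm and *p* = 70%, one voided patient moves the proportion by 0.70/6 = 11.7 points.

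**The trigger sentence.** Consider a patient who takes a prohibited analgesic before 72 hours without prior rescue. Section 8.1 says that prohibited drug use is generally not a reason for discontinuation, so neither event in the third sentence of section 13.1.6 need occur. The first sentence nevertheless makes the 72-hour value missing, and the second imputes missing data by BOCF, which gives a change of 0. Were the patient left out instead, with mean fall *m* among the other 13, the arm mean would be *m* rather than 13*m*/14, a shift of *m*/14. For an assumed *m* of 40 to 60 mm that is 2.9 to 4.3 mm. As a yardstick, the plan's 20 mm reproduces as the smallest significant observed difference: t(0.975, 26) × 26 × √(2/14) = 20.2 mm. The shift is 14% to 21% of 20 mm. Analgesics taken after failed rescue are not affected, because BOCF has already started.

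**The case against.** The strongest answer is that the protocol holds only the main provisions. Sections 13.1.7 and 13.5.3 defer detail to a separate statistical analysis plan, to be approved before the interim data lock and not part of the text supplied. Section 13.1.6 also defers incomplete data for all other variables to it, although that sentence stands under a heading for other data, set against efficacy data, so its reach over this endpoint is arguable. This stands in part: the missing rule is shown for the protocol only. The voiding rule, however, is already fixed there.

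A reader might infer that the plan orders BOCF for an endpoint without a baseline. It does not: BOCF is confined to the main efficacy analysis. A reader might also infer that the plan has chosen an observed-case denominator. It has not: sections 13.1.1 and 13.5.1 together can be read as the whole efficacy population, with a patient who has no valid rating simply outside the numerator. That reading is permitted but not stated.

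A global rating immediately before rescue is required (sections 9.8.2, 10.4 and 11.4.2; Table 3.1, footnote 25), so the patient's view at failure is collected. No section says how it is to be used.

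Finally, the stakes are limited. The endpoint is secondary and receives frequency tables only, section 13.7 plans no formal hypothesis testing, and the study is open-label and exploratory. This stands and sets the priority.

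**Conclusion.** The point holds as a gap in the rule for the global assessment. Following the protocol text, an analyst could drop treatment failures from the Excellent/Good proportion without departing from the plan. On the assumed rates the proportion in one arm would be overstated by 7 to 34 points, and a difference of 14 to 23 points between arms could be shown as none. The documents give no rescue, prohibited-analgesic or response rates, so these figures show how sensitive the table is and do not forecast the result.

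It is tempting to conclude that users of prohibited analgesics fall out of the primary analysis. The documents do not support that: the first two sentences of section 13.1.6 already lead to BOCF for them, and the third, which reads as explanation, merely fails to match. That part is a wording clean-up. Overall this is a cheap improvement of low to moderate priority.

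**What to change.** In section 13.5.3 or the separate statistical analysis plan, before the interim data lock:

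1. Count a patient as not Excellent/Good at every time point after rescue, a prohibited analgesic or withdrawal, with the efficacy population of section 13.1.1 as denominator.
2. Show isolated missed ratings as their own category and do not merge them with failures. Diclofenac patients need not attend on Days 10, 18 and 22, and diclofenac outpatients may rate at home at 4 and 8 hours (Table 3.1, footnotes 3, 26 and 29). If home ratings are missed more often, a missed-equals-failure rule would fall unequally on the comparator.
3. Add an observed-case table as a sensitivity display.

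As a minor correction, add prohibited analgesic use to the third sentence of the efficacy paragraph in section 13.1.6 so that it matches the first, and say what the main efficacy analysis is.

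The cost is a few sentences and little programming; no new data are needed and the sample size is unchanged. The drawback is a visibly lower stated response, by the one-arm gaps shown in the working.

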#### Other data

Details reflecting incomplete data for assessment of all other variables will be described in the statistical analysis plan compiled and approved before the data lock point for interim analysis.

# 13.1.7 Deviations from the statistical analysis plan

The main provisions of the statistical analysis are described in this Study Protocol. More details on the statistical analysis plan will be presented in a separate document compiled and approved before the data lock point for an interim analysis. All deviations from the statistical analysis plan will be described in the Report for this clinical study.

CONFIDENTIAL P. 72 of 84

# 13.1.8 Demographics, information concerning the primary disease, and other baseline parameters

The body weight index will be calculated for the patient based on the height and weight before the start of the investigational product use.

Demographic and underlying disease information will be presented using descriptive statistics by treatment group for all patients in the safety population.

Baseline parameters will include all measurements related to the efficacy and pharmacodynamics, performed on Day 1 prior to the first investigational product administration.

Baseline parameters related to the pharmacodynamic assessment will be presented using descriptive statistics by treatment group for all patients in the pharmacodynamic population.

Baseline parameters related to the efficacy assessment will be presented using descriptive statistics by treatment group for all patients in the efficacy population.

## 13.1.9 Concomitant therapy

Concomitant drugs will be coded according to their international nonproprietary names, using the WHO drug terminology. Standard frequency tables and a list of data for all patients in the safety population will be presented.

# 13.2 Pharmacokinetic analysis

All types of pharmacokinetic analysis will be conducted for the pharmacokinetic population.

The following parameters will be assessed to analyze the pharmacokinetic properties of the investigational product after single dose administration using a non-compartmental approach:

- AUC0-t
- AUC0-∞
- Cmax
- tmax
- t1/2
- Kel

CONFIDENTIAL P. 73 of 84

# 13.3 Analysis of anti-drug antibody levels

An analysis of anti-drug antibody levels will be carried out in all patients who have received RPH-104. Information on anti-drug antibody levels will be presented by end point, treatment group, and for all patients regardless of treatment group, using descriptive statistics.

A list of all measured anti-drug antibody levels will be compiled.

## 13.4 Pharmacodynamic analysis

#### Pharmacodynamic variables

- Change in serum hs-CRP levels at 24, 72 hours, 5, 6, 15, 29 and 45 days after start of the investigational product therapy compared to baseline.
- Changes in the level of amyloid A protein in the blood serum at 24, 72 hours, days 5, 6, 15, 29 and 45 after start of the investigational product therapy compared to baseline.
- Change in serum cytokine (IL-1α, IL-1β, IL-1RA, IL-6, IL-8, TNF-α) levels at 24, 72 hours, 5, 6, 15, 29 and 45 days after start of the investigational product therapy compared to baseline.

# Analysis of pharmacodynamic data

The levels of hs-CRP, serum amyloid protein A and cytokines will be presented by measured parameters, measurement points and treatment groups using descriptive statistics.

For hs-CRP, serum amyloid protein A, and cytokines, graphs of changes in the concentration of these substances versus time for the treatment groups will be plotted.

Model mean changes (least squares means) in hs-CRP, serum amyloid protein and cytokine levels from baseline and confidence intervals for pairwise differences between each RPH-104 group and Voltaren® (diclofenac) group will be presented for each parameter and measurement point using ANCOVA with the baseline value of the parameter as a covariate.

All measured hs-CRP, serum amyloid protein A and cytokine levels will be presented as lists.

### 13.5 Efficacy analysis

#### 13.5.1 Efficacy endpoints

#### Primary efficacy endpoint

Change in pain intensity in the assessed joint at 72 hours after start of the investigational product therapy compared to baseline, as measured on the visual analogue scale (VAS).

# Secondary efficacy endpoints

- Change in pain intensity in the assessed joint at 15, 30, 45 minutes, 1, 1.5, 2, 4, 8, 24, 48, 72 hours, on days 5, 6, 10, 15, 18, 22, 29 and 45 after start of the investigational product therapy compared to baseline (as measured on VAS).
- Proportion of patients who rated the response to the investigational product therapy as "Excellent" or "Good" at 15, 30, 45 minutes, 1, 1.5 hours, 2, 4, 8, 24, 48, 72 hours, on days 5, 6, 10 15, 18, 22, 29, and 45 after initiation of the investigational product therapy;
- Change in the degree of swelling, tenderness, erythema in the assessed joint at 24, 48, 72 hours, on days 5, 6, 10, 15, 18, 22, 29 and 45 after start of the investigational product therapy compared to baseline;

CONFIDENTIAL P. 74 of 84

- Change in movement restriction in the assessed joint at 24, 48, 72 hours, on days 5, 6, 10, 15, 18, 22, 29 and 45 after start of the investigational product therapy compared to baseline:
- Time to 50% reduction in pain intensity in the assessed joint relative to the baseline level according to the VAS;
- Time to use of the rescue medication
- The proportion of patients who received the rescue medication within 72 hours of starting the investigational product therapy and over the entire treatment period;
- Changes in the health assessment questionnaire scores 2, 4, and 6 weeks after start of the investigational product therapy compared to baseline.

## 13.5.2 Analysis of the primary efficacy endpoint

The results of the primary endpoint assessment will be presented using descriptive statistics.

The confidence intervals for the change in pain intensity on VAS in each treatment group will be calculated by ANCOVA using the baseline values and treatment group as covariates.

As supplemental analyses for the primary endpoint, model mean values (least squares means) of changes in pain intensity and confidence intervals for pairwise differences between each RPH-104 therapy group and Voltaren® (diclofenac) group will be presented using ANCOVA model with factors of the baseline pain intensity score and baseline body mass index (BMI) as covariates.

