#### 4 STUDY RATIONALE AND GOAL

The present study is a phase IIa study. This study aims to evaluate the efficacy, pharmacokinetics, pharmacodynamics, safety and tolerability of RPH-104 following a single injection in adult patients with an acute gout attack.

To clarify certain aspects of conducting a clinical trial, the following changes have been made to this protocol compared to the previous version 6.0 of June 6, 2019:

• An interim analysis of data from patients randomized as of November 2020 was included.

Rationale for change: Due to the low rate of enrollment in the study (between March 2018 and November 2020, 47 patients [~55% of the planned sample size] were enrolled in the study) and the negative impact on enrollment of the COVID-19 pandemic, the sponsor decided to conduct an interim analysis of the data of 47 patients included in the study as of November 2020 in order to assess the feasibility of continuing the recruitment and further conducting the study. All patients whose data will be included in the interim analysis completed their participation in the study; follow-up is not required in the study. The interim analysis will include the efficacy, safety, pharmacokinetics and pharmacodynamics data available and verified at the time of analysis. An interim report based on the results of the analysis may become final. In case of early termination of the study, the sponsor will send respective notifications to the investigators and the regulatory authorities.

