#### 6.2 Study design and study design flowchart

This clinical study is a multicenter, open-label, single-dose, parallel-group, two-period, randomized, phase IIa study to assess the efficacy, pharmacokinetics, pharmacodynamics, safety and tolerability of the investigational product RPH-104.

In study Period 1, eligible patients are enrolled in a group of 22 patients and randomized to receive either RPH-104 4 mg or Voltaren® (diclofenac) in a 15:7 ratio (15 RPH-104 : 7 Voltaren® (diclofenac)). Patients using Voltaren® (diclofenac) will receive the concomitant drug Ortanol® (omeprazole) in order to prevent damage to the gastric or duodenal mucous membrane.

Upon completion of the enrollment of 22 patients, study Period 2 starts. In Period 2, newly enrolled patients are randomly assigned to one of 5 treatment groups: RPH-104 20 mg, 40 mg, 80 mg and 160 mg and active control (Voltaren® (diclofenac)). It is planned to include 14 patients in the RPH-104 groups in Period 2, and 7 patients in the Voltaren® (diclofenac) group.

The enrollment of patients in Period 1 and Period 2 is sequential. There is no pause between the enrollment of patients in Period 1 and Period 2. Thus, patient enrollment for study Period 2 begins immediately after all Period 1 patients are enrolled. Information on the planned total number of patients in the treatment groups is presented in Table 6.1.

CONFIDENTIAL P. 35 of 84

Table 6.1 Number of patients by treatment groups

Treatment group	Study therapy	No. of patients
RPH-104 4 mg	RPH-104, 4 mg, SC, single dose	15
RPH-104 20 mg	RPH-104, 20 mg, SC, single dose	14
RPH-104 40 mg	RPH-104, 40 mg, SC, single dose	14
RPH-104 80 mg	RPH-104, 80 mg, SC, single dose	14
RPH-104 160 mg	RPH-104, 160 mg, SC, divided into 2 injections, 80 mg each at different injection sites	14
Voltaren® (diclofenac)	Voltaren® (diclofenac) 50 mg 3 times a day for 3 days, then 25 mg 3 times a day for 9 days	7 in Period 1 and Period 2 each, total of 14 patients
Total	'	85

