# 6.3 Subjectivity minimization measures

#### 6.3.1 Randomization

In Period 1, eligible patients are randomized to receive either RPH-104 4 mg or Voltaren® (diclofenac) in a 15:7 ration, i.e. 15 RPH-104 : 7 Voltaren® (diclofenac)).

In Period 2, eligible patients are randomized to receive either RPH-104 20 mg, 40 mg, 80 mg and 160 mg or Voltaren® (diclofenac) in a 2:2:2:2:1 ratio, respectively.

A summary of the treatment groups and the number of patients per group is provided in Table 6.1.

The randomization will be carried out on the basis of a pre-generated randomization list with a random sequence of randomization of patients generated by the software.

CONFIDENTIAL P. 37 of 84

The patient will be randomized by assigning the patient a number and a short name of the therapy group, for example, RPH-104 4 mg. An Interactive Web Response System (IWRS) with technical support service will be used to randomize the patient. Randomization is carried out by the investigator Information about the patient group assigned at randomization is to be recorded in the source documentation.

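### The 72-hour comparisons of each dose with diclofenac pool controls from two sequential randomisations, and no period-adjusted version is described

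*Combined protocol and SAP*

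**What the plan says.** Section 6.2 sets out two consecutive randomisations. In Period 1, 22 patients are allocated 15:7 to RPH-104 4 mg or diclofenac. "Upon completion of the enrollment of 22 patients, study Period 2 starts", and the arms change: "In Period 2, eligible patients are randomized to receive either RPH-104 20 mg, 40 mg, 80 mg and 160 mg", or diclofenac, with weights 2:2:2:2:1 (section 6.3.1). Table 6.1 lists the diclofenac arm as "7 in Period 1 and Period 2 each, total of 14 patients". On timing, section 6.2 adds: "There is no pause between the enrollment of patients in Period 1 and Period 2".

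For the primary endpoint, section 13.5.2 plans descriptive statistics and a within-group interval from an ANCOVA with baseline and treatment group. As supplemental analyses it plans least-squares means and "confidence intervals for pairwise differences between each RPH-104 therapy group and Voltaren® (diclofenac) group", which "will be presented using ANCOVA model with factors of the baseline pain intensity score and baseline body mass index (BMI) as covariates". The combined document describes no period term, no stratification by period and no concurrent-control comparison, either here or for the pharmacodynamic ANCOVA (13.4) or the repeated-measures model (13.5.3). Sections 13.1.7 and 13.5.3 leave further detail to a separate SAP, to be approved before the interim data lock.

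On calendar time, section 4 reports that "between March 2018 and November 2020, 47 patients [~55% of the planned sample size] were enrolled in the study". On the 47-patient analysis it says: "An interim report based on the results of the analysis may become final".

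**The concern.** No patient could be allocated to both 4 mg and a higher dose. The randomised control group for 4 mg is the 7 Period 1 diclofenac patients; for 20 to 160 mg it is the 7 Period 2 diclofenac patients. Pooling all 14 brings into every contrast controls who were not randomised alongside that dose.

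If the 72-hour change differs between periods for reasons other than treatment, and baseline pain and BMI do not absorb the difference, the pooled contrasts are biased. The bias runs in opposite directions for 4 mg and for the other doses, so it also distorts how 4 mg looks relative to the rest. Section 13.7 plans a descriptive reading of dose dependence, which sets 4 mg beside doses it was never randomised against.

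Two features make this worth a check. Accrual of the first 47 patients was slow, so the periods may be well separated in calendar time even without a pause; the date Period 1 ended is not given. And the outcome is a patient-reported score in an open-label trial, where section 6.3.2 accepts that knowing the drug may influence ratings.

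**Working it through.** **Inputs.** SD of the 72-hour change 26 mm (13.1.2), used here as the residual SD. Group sizes from Table 6.1: 4 mg 15, other doses 14 each, diclofenac 7 + 7. Interim size 47 (13.7). *Assumed:* a shift d (Period 2 minus Period 1) common to all arms and left after covariate adjustment. The documents give no value for d.

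**The plan's own figures.**
- Full width of the per-group 95% interval: 2 × t(0.975, 13) × 26/√14 = 30.0 mm, matching the stated 30 mm.
- Smallest significant pairwise difference: t(0.975, 26) × 26 × √(1/14 + 1/14) = 20.2 mm, matching the stated 20 mm.

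Both reproduce. The second counts diclofenac as one group of 14.

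**Bias of the pooled contrast.** With c1 and c2 diclofenac patients in Periods 1 and 2, the pooled control mean carries d × c2/(c1 + c2). So:
- 4 mg minus diclofenac: bias = -d × c2/(c1 + c2)
- 20 to 160 mg minus diclofenac: bias = +d × c1/(c1 + c2)

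At 85 patients, 7/14 = 0.5, giving -0.5d and +0.5d.

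At 47, assume Period 1 filled 15:7. Then 47 - 22 = 25 patients are in Period 2, with expected diclofenac 25/9 = 2.78 and 50/9 = 5.56 per dose. The non-concurrent share for 20 to 160 mg is 7/9.78 = 71.6%, giving about +0.72d, and -0.28d for 4 mg. Actual counts and block size are not stated. With 1 to 5 Period 2 controls (about 90% of outcomes under simple 1/9 allocation) the share runs from 88% down to 58%.

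**Standard errors.** Pooled SE = 26 × √(1/n + 1/(c1 + c2)). With a period term, and before covariates, the contrast uses only the concurrent controls: 26 × √(1/n + 1/c), where c is c1 for 4 mg and c2 for the other doses. Half-widths use t with 77 (pooled) and 76 (adjusted) df at 85, and 39 and 38 df at 47.

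| Data set | Contrast | SE pooled → adjusted (mm) | 95% half-width pooled → adjusted (mm) |
|---|---|---|---|
| 85 | 20–160 mg | 9.83 → 12.04 | 19.6 → 24.0 |
| 85 | 4 mg | 9.66 → 11.90 | 19.2 → 23.7 |
| 47 (expected) | 20–160 mg | 13.81 → 19.11 | 27.9 → 38.7 |
| 47 (expected) | 4 mg | 10.69 → 11.90 | 21.6 → 24.1 |

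At 47, the adjusted half-width for 20 to 160 mg runs from 33.3 mm (5 Period 2 controls) to 56.9 mm (1 control). With none it cannot be estimated (probability about 5% under simple allocation).

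**Coverage of the pooled 95% interval** (noncentral t, noncentrality = bias/SE):

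| Data set | Contrast | d = 5 mm | d = 10 mm | d = 15 mm |
|---|---|---|---|---|
| 85 | 20–160 mg | 94% | 92% | 88% |
| 47 (expected) | 20–160 mg | 94% | 92% | 88% |
| 85 | 4 mg | 94% | 92% | 88% |
| 47 (expected) | 4 mg | 95% | 94% | 93% |

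**When adjustment wins on mean squared error.** The threshold is |d| = √(SE_adj² - SE_pooled²)/|bias coefficient|, which equals the SE of the between-period diclofenac difference:
- 85: 26 × √(1/7 + 1/7) = 13.9 mm
- 47: 26 × √(1/7 + 9/25) = 18.4 mm (15.2 to 27.8 mm with 5 down to 1 Period 2 controls)

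The 95% half-width of that difference is 27.7 mm at 85 and 37.3 mm at 47.

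**The case against.** The case for leaving the plan alone is substantial.

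- **No drift is shown.** There is no pause between periods, one set of eligibility criteria and one assessment schedule apply throughout, and the March 2018 to November 2020 span covers all 47 patients rather than a gap between periods.
- **The sentence is a summary.** It does not name treatment group either, so its silence on period is weak evidence. The separate SAP was not available and may already deal with period.
- **The arithmetic favours pooling** unless the residual shift is large next to the 20 mm difference used in section 13.1.2.
- **The check has little power.** A true 15 mm shift would give a significant by-period diclofenac difference only about 19% of the time at 85 and 12% at 47.
- **The stakes are limited.** The analysis is supplemental, the study exploratory, and no formal testing is planned.

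All of this stands. It rules out replacing the pooled analysis and keeps the priority modest. It does not remove the point: the planned outputs are estimates and intervals, which are what a shift would distort, and the combined document describes no contrast that uses only the controls randomised alongside each dose. The low power means that a small observed difference would not rule out drift, and that a chance gap could be mistaken for it.

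**Conclusion.** The concern holds, as a modest risk to the supplemental estimates and intervals that should be fixed. At 85 patients, 50% of the controls for every dose are non-concurrent. At the 47-patient analysis, which may be the last, the expected share for 20 to 160 mg is about 72%, provided Period 1 filled as planned and Period 2 followed its ratio. An assumed 10 mm shift would move the contrasts at 85 by 5 mm in opposite directions, putting 4 mg 10 mm out relative to the higher doses, and would lower pooled coverage to about 92%. The size of any real shift is unknown. The statement that period is not addressed is limited to the combined document. Confidence is medium for these reasons.

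**What to change.** Before the interim data lock, pre-specify the following in the separate SAP if it does not already contain them:

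1. A sensitivity version of the 72-hour pairwise ANCOVA in section 13.5.2, with treatment group, baseline pain, baseline BMI and period (1 or 2) as a fixed factor, reported beside the pooled result and not in place of it.
2. A table of the diclofenac 72-hour results by period, with a note that a small difference does not exclude drift.
3. A statement that any comparison of 4 mg with the higher doses is not randomised.
4. What will be reported if the interim data contain no Period 2 diclofenac patients, since the adjusted contrast for 20 to 160 mg then cannot be estimated.

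For the primary endpoint this costs one model and one table, with no new data. The price is precision in the sensitivity result, as tabulated above. Extending it to the pharmacodynamic ANCOVA in section 13.4 (8 analytes × 7 time points) and the repeated-measures model in section 13.5.3 (19 VAS time points) is optional and costs more.
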